7. APPENDIX

7.1 Appendix B1 Partial date conventions for AEs

Missing type	Action
If only the day part of the AE onset date is missing	If the month and year are the same as that of first dose of study medication, the date of first dose of study medication will be used as the onset date of the AE. Otherwise, the first day of the month will be used to complete the onset date of the AE
If the day and month parts of the AE onset date are missing	If the year is the same as that of the first dose of study medication, the date of the first dose of study medication will be used as the onset date of the AE. Otherwise, January 1 st will be used to complete the onset date of the AE.
If the AE onset date is completely missing	The date of the first dose of study medication will be used as the onset date of the AE.
If only the day part of the AE end date is missing	The last day of the month will be used to complete the end date of the AE.
If the day and month parts of the AE end date are missing	December 31 st will be used to complete the end date of the AE.
If the end date of the AE is completely missing and the AE is not ongoing, and the onset date of the AE occurs after the date of the first dose of study medication,	Then the onset date of the AE will be used as the AE end date. Otherwise, the date of the first dose of study medication will be used as the AE end date.

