- Approximately 77 patients will be randomly assigned across 2 treatment groups in a 5:2 ratio to receive either subcutaneous (SC) administration of EQW 2 mg or placebo

(PBO), respectively, with at least 50 patients in the exenatide and at least 20 patients in the PBO group.

- Group A: EQW 2 mg (52 weeks)
- Group B: PBO (24 weeks), EQW 2 mg (28 weeks)
- The study includes a 24-week, controlled assessment period, during which patients will receive study medication according to their randomized treatment group, followed by a 28-week, open-label, uncontrolled extension period in which all patients will receive EQW.
- In addition to receiving study medications, all patients will participate in a lifestyle intervention program encompassing diet and physical activity modifications. If patients are taking concomitant antidiabetic medication they should administer their usual concomitant antidiabetic medication therapy at approximately the same time each day throughout the study.
- At Visit 1 (Screening), patients will complete eligibility evaluations and screening procedures. Patients who meet eligibility requirements will be randomly assigned to a treatment group (Group A: EQW 2 mg, Group B: PBO) at Visit 2 (Week 0). At Visit 2 (Week 0), patients will complete baseline safety, efficacy, pharmacodynamic (PD), and pharmacokinetic (PK) assessments. Following baseline assessments, patients and parents/caretaker will be trained on study medication administration and the first dose of study medication will be administered. During the controlled assessment period, patients or parent/caretaker will administer study medication. Patients will return to the study site at 4- or 6-week intervals for safety, efficacy, PD, and PK assessments. On weeks with no scheduled study-site visits, patients may opt to return to the study site to have the injection procedure monitored or provided by study-site personnel.
- Following the 24-week controlled assessment period, all patients will enter the 28-week extension period. During the 28-week extension period, all patients will receive EQW 2 mg for 28 weeks up to Visit 10 (Week 52/End of Treatment). The patients will return to the study site at 6- or 12-week intervals for safety, efficacy, PD, and PK assessments and will complete study termination procedures at Visit 11 (Week 62/Study Termination).

The overall study design is shown [below](#).

Randomization 5:2

Abbreviations: EQW, exenatide once weekly; P, phone call

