Note: All visits scheduled during the controlled assessment period and during the extension period should occur within ±2 days of the scheduled date, relative to Visit 2 (Week 0).

Visit 11 must occur at least 10 weeks from final dose but no more than 12 weeks.

The Investigator and/or qualified study-site personnel will contact patients by phone at Week 2, Week 16, and Week 26 to discuss study compliance, address questions related to study medication, and review adverse events.

- All patients will have Visit 11 (Week 62/Study Termination) which is a follow-up visit occurring 10 weeks after the last dose administration at Visit 10 (Week 52).
- Following Visit 11 (Week 62/Study Termination), patients whose height increase is at least 5 mm between Visit 8 (Week 28) and Visit 11 (Week 62/Study Termination) will participate in an Extended Safety Follow-up Period. Patients who discontinue study medication prior to Visit 11 (Week 62) will also participate in the Extended Safety Follow-up Period, unless they have a height increase of less than 5 mm over a 6-month interval at study-site visits prior to discontinuation of study medication. Patients who do not have height assessments at study-site visits over a 6-month interval prior to discontinuation of study medication will enter the Extended Safety Follow-up Period.
- The Extended Safety Follow-up Period will continue for up to 3 years or until the increase in height between two 6 month interval visits is less than 5 mm (whichever comes first). No study medication will be administered during the Extended Safety Follow-up Period.

Target Patient Population

A total of 77 male or female children and adolescents of 10 to <18 years of age, diagnosed with type 2 diabetes mellitus and treated with diet and exercise alone or in combination with a stable dose of an oral antidiabetic agent (metformin and/or sulfonylurea [SU]) and/or insulin

for at least 2 months prior to screening, will be randomized into this study to yield 70 evaluable patients.

Key Inclusion Criteria

Each patient must meet the following criteria to be enrolled in this study.

1. Is a child or an adolescent of 10 to <18 years old, at Visit 1 (Screening)
2. Has been diagnosed with type 2 diabetes mellitus per American Diabetes Association diagnostic criteria
3. HbA1c of 6.5% to 11.0%, inclusive, in patients not taking insulin/SU, and of 6.5% to 12.0%, inclusive, in patients taking insulin/SU, at Visit 1 (Screening)

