Abbreviations: EQW, exenatide once weekly; P, phone call

Note: All visits scheduled during the controlled assessment period and during the open-label extension period should occur within ± 2 days of the scheduled date, relative to Visit 2 (Week 0).

Visit 11 must occur at least 10 weeks from final dose of study medication but no more than 12 weeks.

The Investigator and/or qualified study-site personnel will contact patients by phone at Week 2, Week 16, and Week 26 to discuss study compliance, address any questions related to study medication, and review adverse events.

Note: The first dose of open-label EQW during the extension period will be given at the Week 24 visit.

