3.6.1 Study baseline

The baseline measurement is defined as the last non-missing (either numerical or character) value, including values from unscheduled visits, collected on or prior to the first dose of study medication in the double-blind treatment period. Assessments carried out on the date of first dose are assumed to have been done pre-dose unless time information indicates otherwise. In case of multiple measurements for a given variable with tied collection date or date/time, the mean of the values will be calculated for baseline. If the baseline value is missing for a given variable, change from baseline will be missing.

For change from baseline summaries of data collected during the extension period, the baseline value will not be rederived.

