3.6.5.2 Safety and concomitant medications

Adverse events, hypoglycemic events and concomitant medications on the date of first dose of open-label EQW (Week 24 visit) will be assigned to the extension period as this is considered a conservative approach. Other safety assessments at the Week 24 visit will be considered to have been carried out pre-dose and will therefore be assigned to the controlled assessment period. This is reflected in the definitions below.

Controlled assessment period:

- For patients who do not enter the extension period, the controlled assessment period will be defined as date of first dose of randomized study medication to date of last dose of randomized study medication + 7 days (or + 90 days after last dose of study medication for reporting of serious adverse events (SAEs) and other clinically significant or related AEs).
- For patients who go on to enter the extension period, the controlled assessment period for all safety parameters except AEs, hypoglycemic events and concomitant medications will be defined as date of first dose of randomized study medication to date of first dose of open-label EQW. For AEs, hypoglycemic events and concomitant medications, the controlled assessment period will be defined as date of first dose of randomized study medication to date of the first dose of open-label EQW – 1 day, in order for AEs, hypoglycemic events and medications recorded on the date of first dose of open-label EQW to be assigned to the extension period.

Extension period: For all safety parameters, except AEs, hypoglycemic events and concomitant medications, the extension period will be defined as date of first dose of open-

label EQW + 1 to date of last dose of open-label EQW + 7 days. For AEs, hypoglycemic events and concomitant medications, the extension period will be defined as date of first dose of open-label EQW to date of last dose of open-label EQW + 7 days (or + 90 days for SAEs and other clinically significant or related AEs). The extension period will only be defined for patients who enter the extension period and receive at least one dose of open-label EQW.

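### In placebo patients who switch to EQW, an AE with only the onset day missing in the switch month is dated to the 1st and nearly always tabulated under placebo, even if it began on EQW

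*SAP*

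**What the plan says.** SAP Appendix B1 treats an AE onset with only the day missing in two branches. The first applies "If the month and year are the same as that of first dose of study medication" and sets the onset to that dose date. For every other month the rule is: "Otherwise, the first day of the month will be used to complete the onset date of the AE".

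The dose named in the first branch is the Week 0 dose. SAP Section 3.6.1 defines baseline from values "collected on or prior to the first dose of study medication in the double-blind treatment period", and Section 3.6.5.2 names the switch dose separately as the first dose of open-label EQW. The note under the design figure in SAP Section 1.2 gives its timing: "The first dose of open-label EQW during the extension period will be given at the Week 24 visit". Visits "should occur within ±2 days of the scheduled date" (Protocol synopsis, note to the study design figure).

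For patients who enter the extension, SAP Section 3.6.5.2 runs the controlled period for AEs "to date of the first dose of open-label EQW – 1 day". AEs on the date of the switch dose itself "will be assigned to the extension period as this is considered a conservative approach".

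SAP Section 4.1.3.3 uses the imputed dates for tabulation. Section 4.2.4.1 presents the AE summaries by study period. Section 4.2.4.2 draws injection-site reactions from the AE dataset, so they follow the same dates.

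**The concern.** A placebo patient who enters the extension starts active drug at Week 24, not at Week 0. Appendix B1 pulls an uncertain onset to the start of dosing at Week 0 but has no counterpart for this second start. In the switch month it moves the onset to the earliest possible day, which is almost always before the first EQW dose.

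An event that began on EQW can then appear in the placebo column of the controlled period and be absent from the extension column of the Placebo -> EQW group. Safety and tolerability against placebo over 24 weeks is a primary objective (Protocol Section 2.1, SAP Section 1.1.1). The placebo arm is small, so single patients move its percentages visibly.

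**Working it through.** The documents state no figure on this point, so there is none to reproduce. The check follows the date rule and then enumerates dates.

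**Inputs**
- Switch at Week 24, that is 168 days after the first dose (SAP Table 3.1 gives target day 169 with first dose as day 1), with the ±2-day visit window: 166 to 170 days.
- Controlled period for AEs ends the day before the switch dose (SAP Section 3.6.5.2).
- Assumption: first-dose dates are all days from 2016 to 2019. This gives 1,461 dates × 5 offsets = 7,305 combinations.
- Assumption: the true onset is uniform over the days of the switch month.

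**Step 1. Can the first-dose exception apply in the switch month?** No. At least 166 days separate the two doses and no month exceeds 31 days. The enumeration finds 0 of 7,305 combinations in the same month.

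**Step 2. Where does the imputed date fall?** It precedes the switch unless the switch is itself on the 1st. The 1st precedes the switch in 96.7% of combinations. In the other 3.3% the AE goes to the extension, correctly.

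**Step 3. How often is the period wrong?** Let the switch fall on day s of a month with m days.
- Share of onsets truly on EQW = (m − s + 1)/m.
- Wrongly credited to placebo = (m − s + 1)/m if s > 1, and 0 if s = 1.
- Wrongly credited to EQW = 0. If s > 1, every such AE goes to placebo; if s = 1, the month has no placebo days.

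Example: first dose 18 January 2017, switch 5 July 2017. An onset known only as July 2017 becomes 1 July, inside the controlled period, which ends on 4 July. Of 31 possible days, 27 are on EQW: 27/31 = 87.1% wrongly credited.

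Range in a 31-day month: 30/31 = 96.8% for a switch on the 2nd, down to 1/31 = 3.2% for a switch on the 31st.

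Average over the 7,305 combinations:

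| Quantity | Share of such AEs |
|---|---|
| Truly began on EQW | 51.6% |
| Began on EQW, counted under placebo | 48.4% |
| Began on placebo, counted under EQW | 0% |

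Of those that truly began on EQW, 48.4/51.6, or 93.6% before rounding, are counted under placebo.

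**Step 4. What is one patient worth?** Placebo patients: 77 × 2/7 = 22. One patient: 1/22 = 4.5 percentage points.

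**Step 5. What does dating to the switch dose do?** In the placebo arm, EQW events counted under placebo fall from 48.4% to 0%. Before any end-date check, 100 − 51.6 = 48.4% become placebo events counted under EQW.

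**The case against.** The number affected is probably very small. Onset date is a collected AE variable, missing data are queried (Protocol Section 10), and AEs are reviewed by telephone at Week 26 and at the Week 28 visit. A patient counts once per preferred term and period (SAP Section 4.3.4.2), so a shifted event need not add a patient to a row. The events stay treatment-emergent, and listings show dates without imputation. Taking the earliest possible date also matches how Appendix B2 completes partial medication start dates. All of this stands and limits the size. It does not make the attribution right when such a date occurs.

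A reader might infer more than the documents support:
- *That the rule lowers the EQW rate in the randomized comparison.* It does not. In the EQW arm the same rule places switch-month AEs in the controlled period, so it can only raise that rate or leave it unchanged. Part of the effect on the between-arm difference is therefore offset.
- *That it hides early gastrointestinal events.* Protocol Section 1.3.1 lists nausea, vomiting and diarrhea without timing, and Section 1.1 describes plasma concentrations rising over about 6 to 8 weeks.
- *That Appendix B1 flatly contradicts the conservative rule.* Section 3.6.5.2 literally covers events on the known switch date. Carrying it to an unknown day is an inference, although Appendix B1 does resolve the doubt in the opposite direction.
- *That every such AE is misassigned.* Only those that began on EQW are, and not when the switch is on the 1st.

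**Conclusion.** The point holds as a minor one, confined to patients randomized to placebo who enter the extension and to AEs lacking only the onset day in the switch month. This is a stated rule that gives a one-sided error in treatment attribution, not merely an omitted detail. It can inflate the placebo controlled-period AE rate and lower the extension rate in the Placebo -> EQW group.

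That the error runs in one direction follows from the rule itself. The 48% figure rests on uniform onset and an even spread of switch dates; for an individual patient it depends on the day of the switch. The effect on the tables cannot be sized, because the documents give no count of partial dates. The 4.5 points is the most that one extra patient can add, not an expected bias.

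**What to change.** Add one clause to the day-missing onset row of Appendix B1. For patients randomized to placebo who receive open-label EQW, if the known month and year equal those of the first open-label EQW dose, use that dose date as the onset date. If a known AE end date is earlier than that dose, keep the 1st of the month.

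Leave the rest as written:
- *EQW arm.* The same clause there would move events that truly began before Week 24 out of the controlled period and lower the EQW rate in the randomized comparison.
- *Year-only and completely missing onset rows.* A year-wide version would collide with the existing year rule whenever the Week 0 dose and the switch share a calendar year, which is about 54% of start dates at day 168.

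The cost is one clause and a small programming change. The downside is that some true placebo events in that month will be counted under EQW. That is the direction Section 3.6.5.2 calls conservative, and the end-date check limits it.

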7.2 Appendix B2 Algorithm for prior /concomitant medications

START DATE	STOP DATE	Action
	Known	
If stop date < study med start date, assign as pre-treatment
 
If stop date \geq study med start date and start date < study med start date, assign as prior concomitant
 
If stop date \geq study med start date and start date \geq study med start date, assign as new concomitant

Known	Partial	
Impute stop date as latest possible date (ie, last day of month if day unknown or 31st December if day and month are unknown), then:
 
Follow the same algorithm above for a known start date and known stop date.

	Missing	
If stop date is missing could never be assumed a prior medication
 
If start date < study med start date, assign as prior concomitant
 
If start date \geq study med start date, assign as new concomitant

	Known	
Impute start date as earliest possible date (ie, first day of month if day unknown or 1st January if day and month are unknown), then:
 
Follow the same algorithm above for a known start date and known stop date.

Partial	Partial	
Impute start date as earliest possible date (ie, first day of month if day unknown or 1st January if day and month are unknown) and impute stop date as latest possible date (ie, last day of month if day unknown or 31st December if day and month are unknown), then:
 
Follow the same algorithm above for a known start date and known stop date.

START DATE	STOP DATE	Action
	Missing	
Impute start date as earliest possible date (ie, first day of month if day unknown or 1st January if day and month are unknown), then:
 
If stop date is missing could never be assumed a prior medication
 
Follow the same algorithm above for a known start date and missing stop date.

	Known	
If stop date < study med start date, assign as pre-treatment
 
If stop date ≥ study med start date, assign as prior concomitant

Missing	Partial	
Impute stop date as latest possible date (ie, last day of month if day unknown or 31st December if day and month are unknown), then:
 
Follow the same algorithm above for a missing start date and known stop date.

	Missing	Assign as prior concomitant

7.3 Appendix B3 Units and marked abnormality criteria for safety laboratory variables and vital sign parameters

Clinical laboratory variables will be summarized using the reference ranges in the lab manual.

Potentially clinically significant changes are assessed with the following marked abnormality criteria for vital signs⁹:

Age: 6 - <12 years

Vital signs variables	Units	Marked abnormality criteria	
		Low	High
Heart Rate			
Value	bpm	< 60	> 95
Value - Baseline	bpm		> 20
Baseline - Value	bpm		>10
Systolic Blood Pressure			
Value	mmHg	< 100	> 120
Value - Baseline	mmHg		> 10
Baseline - Value	mmHg		>10
Diastolic Blood Pressure			
Value	mmHg	< 60	> 75
Value - Baseline	mmHg		> 10
Baseline - Value	mmHg		>10

Age: ≥12 years

Vital signs variables	Units	Marked abnormality criteria	
		Low	High
Heart Rate			
Value	bpm	< 55	> 85
Value - Baseline	bpm		> 20
Baseline - Value	bpm		>10
Systolic Blood Pressure			

Vital signs variables	Units	Marked abnormality criteria	
		Low	High
Heart Rate			
Value	mmHg	< 110	> 135
Value - Baseline	mmHg		> 10
Baseline - Value	mmHg		>10
Diastolic Blood Pressure			
Value	mmHg	< 65	> 85
Value - Baseline	mmHg		> 10
Baseline - Value	mmHg		>10

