3.6.4 Rescue therapy

Rescue therapy is defined as any new concomitant medication (see Section 4.2.1.4 for detail) with therapy reason given as “Protocol defined exacerbation of disease under study”.

A rescue episode will be defined as the first unique rescue therapy entry on the CM eCRF. If a patient has multiple entries on the CM form flagged as a rescue therapy, the first will be considered the point at which the patient was rescued.

Increases in insulin from baseline in patients receiving insulin at baseline will be programmatically derived from the CM CRF and reviewed by the clinical team prior to unblinding. Increases identified as potential rescue episodes will be queried at the site-level and therapy reason may be updated to “Protocol defined exacerbation of disease under study”.

For patients who require initiation of rescue therapy and continue study treatment, only data before initiation of rescue therapy will be included in the primary efficacy analysis. If HbA1c is measured before rescue therapy, then we will include the HbA1c measurement. If HbA1c is measured on the date of first rescue therapy but no time information is available to indicate if it was taken before rescue therapy, then HbA1c will be assumed to be prior and included in the primary efficacy analysis. Sensitivity analyses including data after initiation of rescue therapy will be carried out to test the robustness of the missing data assumption.

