4.1.3.3 Missing safety data

Safety analyses will be conducted on the observed data only.

However, imputation of missing or partial AE and concomitant medication onset/start and end/stop dates will be used to determine the status of each AE and the previous/concomitant status of each medication. Refer to [Appendix B1](#) and [B2](#) for the method of imputation of missing/partial AE/concomitant onset/start and end/stop dates. Missing/partial start/stop dates will appear as is (i.e., without imputation) in the patient data listings, but will be imputed to permit the proper tabulation of AE and concomitant medications data.

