Antidiabetic concomitant medications will be summarized separately by chemical/pharmacological/therapeutic subgroup (ATC level 4) and generic term in the same manner.

Background insulin therapy use during the study will be summarized as outlined in Section 3.6.5 for long-acting, short-acting and overall total daily insulin dose. Data collected after discontinuation of study medication will be excluded.

Rescue medications will be summarized during the controlled assessment period for the ITT analysis set and separately during the extension period separately for the subset of ITT patients who received open-label EQW.

A listing for rescue medications will be provided.

Pre-treatment medications and post-treatment medications will be summarized separately by treatment and ATC classification for the ITT analysis set.

Medications with start/stop dates that are partially/completely missing will be imputed as described in [Appendix B2](#).

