4.2.3.3 Analysis of primary variable

The MMRM analysis of the primary endpoint in the Evaluable population will be considered the primary analysis.

The primary efficacy analysis will compare treatment groups (EQW vs. PBO) with respect to change in HbA1c from baseline (Visit 2 [Week 0]) to Visit 7 (Week 24) by using the MMRM approach. The model will include change in HbA1c as the dependent variable and treatment group, visit, interaction between visit and treatment, region, baseline HbA1c and interaction between visit and baseline HbA1c as the fixed effects. The variance - covariance structure to be used for this modelling will be unstructured (UN); if the model does not converge with unstructured variance – covariance matrix, then autoregressive order 1 (AR [1]) and heterogeneous autoregressive order 1 (ARH [1]) structures will be tried and the covariance structure will be decided based on model convergence status and the Akaike information criterion. The restricted maximum likelihood (REML) method will be used for parameter estimation, and the Kenward-Roget adjustment will be applied (ddfm=KR option in SAS PROC MIXED model statement. The least squares (LS) mean, 2-sided 95% confidence interval, and p-value of the difference in the change of HbA1c between the EQW and PBO groups at Visit 7 (Week 24) will be provided. The mean (SD) observed HbA1c at baseline and Week 24 will also be given by treatment group.

HbA1c data from post-baseline visits (including Early Termination) will be included in the MMRM analysis. See Section 4.1.3 for details on missing data handling.

For patients who initiate rescue medication or discontinue IP and continue study participation, only data before initiation of rescue medication or up to and including date of discontinuation from IP will be included in the MMRM analysis. If there is evidence that a measurement was taken prior to initiation of rescue medication, then this data will be included. If the measurement was taken on the date of initiation of rescue medication but time information is not available, then the measurement will be included. Namely, the data after initiation of rescue medication or after premature IP discontinuation will be excluded from the primary analysis.

Summaries and descriptive analysis of the primary endpoint will be performed using the Evaluable analysis set.

Subgroup analyses of primary endpoint

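### Under SAP Appendix B2 a rescue drug with no start date, or with only the year known, can stop counting as rescue, which would leave post-rescue HbA1c in the primary analysis

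*SAP*

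**What the plan says.** - **Rescue definition (SAP 3.6.4).** "Rescue therapy is defined as any new concomitant medication (see Section 4.2.1.4 for detail) with therapy reason given as" the protocol-defined worsening of the disease under study. Both parts are needed: *new* status and the reason code.
- **What counts as new (SAP 4.2.1.4).** In the controlled period, a start date on or after the first randomized dose.
- **Incomplete dates (SAP 4.2.1.4).** "Medications with start/stop dates that are partially/completely missing will be imputed as described in" Appendix B2. Rescue drugs are not exempted.
- **Appendix B2 (SAP 7.2).** For a partial start date: "Impute start date as earliest possible date (ie, first day of month if day unknown", or 1 January if day and month are both unknown. If the resulting date precedes first dose and the drug did not stop before first dose, the action is "assign as prior concomitant". With no start date at all, the record is *prior concomitant*, or *pre-treatment* if it stopped before first dose. No branch for a missing start date leads to *new*.
- **Use in the primary analysis (SAP 4.2.3.3).** "the data after initiation of rescue medication or after premature IP discontinuation will be excluded from the primary analysis".
- **Only rescue-specific timing rule (SAP 3.6.4).** "If HbA1c is measured on the date of first rescue therapy but no time information is available", the value is kept. Nothing covers an incomplete rescue date.

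**The concern.** A status rule written for medication tables also decides whether a record is rescue at all. A record carrying the rescue reason code cannot sensibly pre-date study treatment, yet B2 can place it there.

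The patient would then be treated as never rescued. HbA1c lowered by the rescue drug would enter the primary model as if it reflected randomized treatment alone, which is not the hypothetical strategy for rescue set out in SAP Table 2. The same misclassification would carry into the other analyses that exclude post-rescue data: the pattern-mixture sensitivity analysis of the primary estimand, the secondary efficacy endpoints (including fasting glucose, body weight and fasting insulin in the testing hierarchy), and the HbA1c goal analyses. The rescue counts and time-to-rescue display would miss the patient as well.

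The gap looks unintended. Appendix B1 moves a partial adverse-event onset to first dose when the known parts match the month or year of first dose; B2 has no such floor. SAP 3.6.6 adds its own rule for insulin records with no start date. Rescue, which sets the cut-off for the primary endpoint, has neither.

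**Working it through.** **1. Trace of the rules for a record with the rescue reason code**

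| Start date on file | Date under B2 | B2 status | Counts as rescue under 3.6.4? |
|---|---|---|---|
| Complete, after first dose | unchanged | new | yes |
| Day missing | 1st of month | new, unless in the calendar month of first dose | usually yes |
| Day and month missing | 1 January | prior if first dose is later in the same year | no, if same year |
| Missing | none | prior, or pre-treatment if stopped before first dose | no |

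**2. How often a year-only date becomes prior**

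The documents give no rescue dates, so these are assumptions. If first dose is spread evenly over the calendar year and rescue starts *r* days later, P(same calendar year) = 1 − mean(*r*)/365.

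- Rescue uniform over Days 30-168: mean 99; 1 − 99/365 = 0.73.
- Rescue uniform over Days 14-167: mean 90.5; 1 − 90.5/365 = 0.75 (simulation 0.75).
- Rescue at the Week 4, 8, 12 or 18 visit: mean (28 + 56 + 84 + 126)/4 = 73.5; 1 − 73.5/365 = 0.80 (simulation 0.796).

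The range is about 73-80%. For a missing start date it is 100%, directly from the rule.

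**3. Size per misclassified patient**

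The plan's own figure comes first. Inputs are from SAP 1.2 and 1.3: 50 and 20 evaluable patients, difference 0.7, SD 1.0, two-sided 5%. The noncentrality is 0.7/(1.0 × √(1/50 + 1/20)) = 0.7/0.2646 = 2.65 on 68 df, giving power 74.2%. The stated 74% is reproduced.

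Now suppose *k* of the 20 placebo patients are misclassified and rescue lowers each one's Week 24 HbA1c by *x*. The treatment difference shrinks by *kx*/20:

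- *k* = 1, *x* = 0.5: 0.025; power 71%.
- *k* = 1, *x* = 1.0: 0.05; power 68%.
- *k* = 3, *x* = 1.5: 0.225; power 42.5%.

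Both *k* and *x* are assumed; the last line is an outer bound, not an expectation.

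**4. Day-missing dates, only if the B2 date were also the HbA1c cut-off**

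With day of month uniform on 1-30, the mean backward shift is 15.5 − 1 = 14.5 days. Taking HbA1c at Weeks 4, 8, 12, 18 and 24, simulation loses at least one valid pre-rescue value in about 38% of such records if rescue falls at random over Days 14-167 (41% over Days 30-168). The figure is about 95% if rescue starts on a visit day, where the same-day value counts as valid under the SAP's tie-break. Only 1-3% become prior.

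**The case against.** The strongest reply is that nothing happens unless a rescue record still has an incomplete date after cleaning, and the documents show no such record. Protocol Section 10 has missing or impossible data queried. Rescue follows confirmation at a clinic visit (Protocol 5.5.3, SAP 4.1.4), so it is not a recalled historical drug. SAP 3.6.4 has potential rescue episodes among insulin increases queried before unblinding, and SAP 5 describes rescue by Week 24 as low. All of that stands, and it makes the risk small. It does not make the rule right: B2 exists because some dates stay incomplete. Rescue may also be started by an outside treating physician with drug the sponsor does not supply.

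A second reply is that SAP 4.1.3.3 limits the imputation to determining status and says dates "will be imputed to permit the proper tabulation of AE and concomitant medications data". This answers only part of the point. Status is exactly what 3.6.4 uses to recognise rescue, so the loss of rescue status needs no further step. It does weaken a stronger reading, that the SAP necessarily deletes valid HbA1c by backdating rescue to the 1st of the month. That requires the B2 date to be the HbA1c cut-off, which no section states; where the authors extend B2 to another derivation, as for insulin dose in 3.6.6, they say so. Backdating is also partly a defensible cautious choice, since it guards against keeping post-rescue values.

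Third, the supplementary estimand in SAP Table 2 keeps post-rescue data and so does not depend on the rescue date. That is correct, but it answers a different question and does not repair the primary analysis.

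**Conclusion.** Wrong as written, minor. The chain from 3.6.4 through 4.2.1.4 to 7.2 is explicit: a rescue-coded record with no start date can never be rescue, and one with only the year known is not rescue whenever 1 January of that year precedes first dose, about 73-80% of the time on the assumed dates.

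The effect on this trial cannot be computed and may be zero. One misclassified placebo patient with a 1.0-point fall would move the difference by 0.05.

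A reader might infer three further things that the documents do not support:
- That HbA1c has actually been wrongly cut or kept. This is conditional on incomplete dates surviving query.
- That a missing start date always means *prior concomitant*. It is *pre-treatment* if the drug stopped before first dose, although neither class counts as rescue.
- That the error flatters exenatide. If placebo has more rescue, retaining rescue-lowered values shrinks the estimated effect and is conservative for superiority; the reverse holds only if exenatide has more rescue.

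Loss of valid pre-rescue HbA1c under a day-missing date is possible, but only on a reading of the cut-off that the SAP does not state.

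**What to change.** Add to SAP 3.6.4 and 7.2:

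1. Any record with the rescue reason code counts as rescue, whatever status Appendix B2 gives it.
2. If its start date is still incomplete after site query, the date is set before unblinding, by staff blinded to treatment, within the interval allowed by the known date parts, first dose and the documented rescue-confirmation visit. It is not defaulted to first dose plus one day, because that would delete valid HbA1c. The same sentence should say that this date is the HbA1c cut-off.

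If any such record exists, repeat the primary MMRM with the earliest and latest plausible rescue dates.

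The cost is one or two SAP sentences, a query for any record concerned and, at most, one extra sensitivity run. If every rescue date is complete, no result changes. The sample size is unaffected.
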